4.2 Exclusion Criteria

Women will be excluded from this study if they meet any of the following criteria at enrollment:

- has a primary partner who has received a vasectomy or is otherwise sterile
- medical contraindications to depot medroxyprogesterone acetate (DMPA) per WHO medical eligibility criteria for contraceptive use [33]
- known HIV-infection (for her or a partner)
- diagnosis or treatment for an STI in the past month (for her or a partner), excluding recurrent herpes or condyloma
- received an injection of a progestin-only containing contraceptive (DMPA or norethisterone enanthate) in the past 12 months

- received an injection of a combined injectable contraceptive in the past 6 months
- known or suspected allergic reaction to DMPA
- used a levonorgestrel intrauterine system, NuvaRing, contraceptive patch, oral contraceptives or a contraceptive implant in the past 7 days (PK cohort only)
- Previous (within 1 month prior to enrollment), current or planned (in the next 12 months) use of an investigational drug, prohibited drug per protocol (see Section 5.3) or other drug which in the opinion of the investigator could complicate study findings
- has been pregnant in the past month
- is lactating
- plans to move to another location in the next 12 months
- has a social or medical condition which in the opinion of the investigator would make study participation unsafe, or interfere with adherence to protocol requirements.

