reports using condoms in the last 4 weeks but not at any other time since last injection, then only the last 4 weeks prior to the report visit will be excluded.

B. Pharmacokinetics Population and Analysis Set

The Pharmacokinetics (PK) Population is a subset of the Treated Population. The PK Population includes participants who agreed to serum MPA testing at 6 timepoints and were randomized into the PK cohort but excludes participants who did not contribute blood specimens for PK assessments, who had a baseline serum MPA concentration exceeding 0.05 ng/mL, or who required the use of more than one Sayana Press unit for their baseline injection (based on information provided on the injection CRF)³. The corresponding Pharmacokinetics Analysis Set will censor data collected after a participant receives an injection in an anatomical site which differs from the site used at enrollment and will exclude any MPA specimens collected during a time when a participant reports using a concomitant medication that may impact the PK of MPA as defined in the protocol. During the coding process, the medical monitor will define the length of the period of exclusion based on participants' use of concomitant medications on a medication-specific basis. The Analysis Set will also exclude MPA results from any blood samples collected after an injection where more than one Sayana Press unit was inserted into the participant's skin (i.e., if a participant had more than one unit inserted at her month 4 injection, then blood samples collected at months 8 and 12 would be excluded from the analysis set for that participant). PK analyses based on this analysis population will be performed according to the site of injection at enrollment, even if it was assigned or was received in error.

VI. Blind Review of Data

As indicated above, neither participants nor center staff will be blinded to injection sites. However, to the extent possible, decisions regarding additions or modifications to planned analyses, determination of exclusion from analysis populations or analysis sets, and rules for handling missing or incomplete data will be made by statisticians, clinicians, or other study staff who do not have access to individual treatment data. The actual level of blinding maintained when performing these activities will be described in the clinical study report.

VII. Analysis of Baseline Data

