Serum MPA concentrations that fall within defined sampling windows (see Appendix A) will be summarized by timepoint and injection site in the following ways: 1) graphically using box plots with whiskers extending to 5th and 95th percentiles, and 2) in tables using means, geometric means, quartiles, minima, maxima, standard deviations, and percent coefficients of variation. A listing of all MPA concentrations for each participant will be provided along with an indication of any that fall outside of defined sampling windows, or any excluded from the PK Analysis Set due to concomitant medication use, injection in an anatomical site different from the site used at enrollment, or insertion of multiple Sayana Press units at the time of injection. The listing will also include subject age and BMI at time of sampling.

Month 2, 3, and 4 data will be used to estimate the apparent half-life for each injection site based on mixed-effects log-linear models with random intercept and slope terms, under the assumption that the terminal phase of absorption begins by month 2.⁵ Unique variance components will be used for each injection site, and observations falling outside sampling windows will not be excluded. The estimated slope (*m*) for each injection site will be used to calculate the apparent half-life according to the following formula: $half-life = \ln(2)/(-m)$. Pharmacokinetics in the terminal phase will be compared across injection sites based on overall and, if significant at the 0.05 level, pairwise Wald-type tests of differences in fixed-effects intercepts and slopes. Differences in variance components (both within-and between-subject effects) will similarly be assessed using likelihood ratio-tests.

Accumulation of MPA concentrations at months 8 and 12 will be estimated for each injection site by calculating the geometric mean ratio (GMR) of trough concentrations at 8 or 12 months to the trough concentration at 4 months, using mixed-effects models to compute 95% CIs of each GMR (with unspecified covariance of log-transformed repeated measures). Any MPA concentrations that are measured more than 7 days past a participant's scheduled injection date (along with any future measurements) will be excluded from the above accumulation

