⁵ This assumption will be formally assessed using appropriate log-linear random-effects model diagnostics, and by comparing predicted month 8 and month 12 concentrations (based on the half-life estimates and 4-month data) with the observed month 8 and 12 concentrations.

analysis. Steady-state accumulation ratios will be estimated as $R = [1 - (0.5)^{\text{dosing interval/half-life}}]^{-1}$, where the dosing interval is assumed to be 126 days and the half-life is estimated in the method described above.

The effects of study center, BMI, and age on trough concentrations will be explored graphically and by incorporating covariates in mixed-effects models based on month 4, 8, and 12 data. Intra-subject variability across injection cycles may also be explored using MPA trough levels at months 4, 8, and 12.

B. Safety

Safety endpoints will include serious adverse events (SAEs), adverse events (AEs) leading to product withdrawal, injection site reactions, bleeding patterns, blood pressure, and body weight recorded at months 4, 8, and final visits. All SAEs, AEs leading to product withdrawal, and AEs which are Grade 1 or higher ISRs will be coded by a trained medical coder at FHI 360 using the Medical Dictionary for Regulatory Activities (MedDRA) to classify them according to preferred term and system organ class (SOC). Safety analyses will be performed using the Treated Population and Safety Analysis Set and will be based on treatment group actually received.

All relevant information on any SAEs will be discussed in the subject narrative included in any clinical study report and in a listing. Numbers and percentages of participants experiencing AEs (specifically AEs leading to product withdrawal and ISRs which are Grade 1 or higher) will be presented by severity, study center, and injection site. Percentages of participants experiencing specified AEs will be compared across injection sites (pooled over severity and study center) within each SOC using Fisher's exact tests. Listings of any AEs will include actual injection site, a description of AE, type of AE, days to onset, relatedness to Sayana Press, seriousness, severity, outcome, and duration. Numbers and percentages of participants experiencing ISRs of any grade will be summarized by injection site, and ISRs will also be presented in a listing.

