Two sensitivity analyses will be performed for the efficacy objective. A Pearl Index and exact 95% confidence interval will be computed per the primary analysis (section IX.B) but excluding any women who had protocol violations occurring at enrollment that warrant exclusion based on blind review. Another Pearl Index and exact 95% confidence interval will be computed per the primary analysis but excluding results from pregnancy tests taken at home and any time between a participant's last in-clinic pregnancy test and her exit from the study. This will assess the impact of final pregnancy tests completed at home in response to the COVID-19 pandemic.

Two sensitivity analyses will be performed for the PK objective. The first will assess the impact of baseline MPA on PK profiles and will include all participants (except for those who required the use of more than one Sayana Press unit) in the PK cohort who provide samples for MPA testing. This will be done in the following way: calculate the half-life (λ) for each injection site using the same method described in the secondary objective above but using the revised population; use that half-life to calculate the concentration at time t (CB_t) due to the baseline amount (C_0) using the following formula

$$CB_t = C_0 e^{-\lambda t};$$

then subtract that amount from the corresponding monthly concentrations for each participant. Summaries of trough concentrations will be provided using these modified values and population.

Secondly, a table summarizing trough concentrations and half-life will be provided for a population comprised of the PK Population plus any participants or samples excluded from the PK Population or Analysis Set based on injection issues (i.e., more than one unit inserted into skin).

XIV. Planned Interim Analyses

An independent DSMB will review interim data when approximately 250 participants have completed 18 weeks of follow-up. This single, pre-planned interim analysis is intended to inform a decision whether to stop or modify the study if the estimated probability of pregnancy pooled across all injection sites is greater than 2% in the first injection interval. Details are provided in a separate DSMB Operational Plan.

XV. MPA Testing of Baseline Serum Specimens

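### SAP XIII labels λ as the half-life in CB_t = C_0·e^(−λt), where the rate constant is needed; taken literally in days, the baseline-MPA correction subtracts nothing

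*SAP*

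**What the plan says.** The main PK analysis leaves out women "who had a baseline serum MPA concentration exceeding 0.05 ng/mL" (SAP V.B). The first PK sensitivity analysis in SAP XIII brings them back and tries to remove the MPA they carried in. The steps are:

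- "calculate the half-life (λ) for each injection site using the same method described in the secondary objective above", refitted with these women included;
- as the next step, "use that half-life to calculate the concentration at time" t, through CB_t = C_0·e^(−λt), where C_0 is the baseline concentration;
- subtract CB_t from each of that woman's later concentrations;
- "Summaries of trough concentrations will be provided using these modified values and population".

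The method referred to is in SAP X.A. A log-linear mixed model is fitted to months 2, 3 and 4, and its slope, m, "for each injection site will be used to calculate the apparent half-life according to the following formula", namely half-life = ln(2)/(−m). The same section then uses the half-life in the steady-state accumulation ratio R = [1 − 0.5^(dosing interval/half-life)]^(−1) and adds "where the dosing interval is assumed to be 126 days and the half-life is estimated in the method described above". There the half-life is a time, in days.

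**The concern.** SAP XIII gives the symbol λ to the half-life and then puts λ in an exponent where only a rate (1/time) makes sense. A half-life multiplied by t has units of time squared. The rate constant is available from the same model as −m, but the text never says to use it.

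Two programmers could therefore get different outputs from one instruction. One reads λ by convention as the rate constant and gets the intended correction. The other follows the definition given and gets troughs that have not been changed at all. The second output would not fail visibly. It would be a table labelled as corrected for baseline MPA, and could be read as showing that baseline MPA makes no difference.

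**Working it through.** The plan states no numerical result for this correction, so there is no figure to reproduce. The check is against the SAP's own half-life formula.

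**Inputs**

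- Half-lives H, from the table in Protocol 1.3.2.1: 43.2 days (site not specified), 80.9 (thigh), 103.7 (abdomen), 247.3 (upper arm, SD 534, so very imprecise). These are background values used as a range; the trial's own estimates are not in the documents.
- Times t, from SAP XVI.A: earliest in-window month 2 sample, day 54; trough target days 119, 245 and 371.
- C_0 = 0.05 and 0.10 ng/mL. These are thresholds in SAP V.B and XV, used only as illustrations.

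**Which quantity belongs in the exponent.** With ln C = a + m·t and m < 0, C_t/C_0 = e^(mt). Setting this to one half gives H = ln(2)/(−m), which is the SAP's formula, so −m = ln(2)/H. Check: after one half-life, e^(−(ln 2/H)·H) = 0.5 for every H. With H itself in the exponent, the fraction after one half-life of 43.2 days would be e^(−43.2×43.2) = e^(−1866).

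**As written, in days.** The largest factors come from the shortest half-life:

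- day 54: 43.2 × 54 = 2332.8, and 2332.8/2.3026 = 1013, so the factor is about 10^−1013;
- day 119: 43.2 × 119 = 5140.8, so the factor is about 10^−2233.

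Both evaluate to exactly zero in double precision, where e^(−x) is zero for x above about 745. This does not depend on the background values: any half-life above 745/54 = 13.8 days gives zero at day 54, and any above 745/119 = 6.3 days gives zero at day 119.

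**Other units.** In months, 43.2 days is 1.42 months and the literal factor at month 4 is e^(−1.42×4) ≈ 0.0034, against 0.148 with the rate constant. In years, it would be e^(−(43.2/365.25)×(119/365.25)) ≈ 0.962. A result that changes with the unit of time confirms that the expression is dimensionally wrong.

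**With λ = ln(2)/H**, the fraction of C_0 remaining is 2^(−t/H):

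| H (days) | ln(2)/H per day | day 119 | day 245 | day 371 |
|---|---|---|---|---|
| 43.2 | 0.0160 | 0.148 | 0.020 | 0.003 |
| 80.9 | 0.0086 | 0.361 | 0.123 | 0.042 |
| 103.7 | 0.0067 | 0.451 | 0.194 | 0.084 |
| 247.3 | 0.0028 | 0.716 | 0.503 | 0.353 |

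**Size for one affected woman at day 119.** For C_0 = 0.10 ng/mL, the amount to subtract is 0.015, 0.036 and 0.045 ng/mL (0.072 upper arm). For C_0 = 0.05 it is half of that. To express this as a share of the trough, extrapolate the published three-month concentrations from day 91 to day 119 as C_3mo·2^(−28/H):

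- 0.40 → 0.255; 0.41 → 0.323; 0.47 → 0.390; upper arm 0.43 → 0.398 ng/mL.
- Shares for C_0 = 0.10: 5.8%, 11.2%, 11.6% (18.0% upper arm).
- If that trough is taken as dose-only and the carry-over is added to the denominator: 5.5%, 10.1%, 10.4% (15.3%).

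**Size for a group.** Assume 10% of women have C_0 = 0.10 ng/mL, the rest none, and every trough sits at the first set of extrapolated values. The day-119 arithmetic mean falls by 0.58%, 1.12% and 1.16% (1.80% upper arm). The geometric mean falls by 1 − (1 − share)^0.10 = 0.60%, 1.18% and 1.22% (1.97%). Read literally in days, the shift is 0.

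**The case against.** This is a slip of notation that is unlikely to be executed literally. λ is the usual symbol for a rate constant, the equation has the correct form for first-order decay, and a half-life is enough information to compute the residual, so the instruction to use it is harmless on its own. SAP X.A handles the half-life correctly in the accumulation ratio, and its footnote 5 has the team predict later concentrations from the half-life estimates. A column of corrected values identical to the originals would probably be noticed.

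The practical effect is also small. The documents give no expected prevalence of baseline MPA, and Protocol 4.2 excludes women who "received an injection of a progestin-only containing contraceptive (DMPA or norethisterone enanthate) in the past 12 months", so few women may be affected.

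Most of this stands and limits the weight of the point. It does not remove it: the text assigns λ to the half-life and then tells the analyst to use that quantity in the formula, and no other section says otherwise. Whether the correction works is left to the programmer's judgement, which an SAP is meant to avoid.

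**Conclusion.** The concern holds as a minor wording error in a stated analysis rule. As written, with time in days, the carry-over correction subtracts zero. With the rate constant, it would subtract 15% to 45% of C_0 at the first trough (up to 72% with the upper-arm half-life), falling to between 0.3% and 8% (35%) by day 371.

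These sizes rest on the SAP's own first-order model with the site half-life applied to C_0, and on the protocol's background half-lives. They are not measured carry-over. The group-level figures rest further on an assumed prevalence and baseline concentration.

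Only the carry-over step of this one PK sensitivity analysis is affected. The effect of restoring women with baseline MPA above 0.05 ng/mL can still be seen without it. The Pearl Index, the main PK analysis, the accumulation ratio and the baseline-testing triggers do not use the formula.

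**What to change.** In SAP XIII, define λ for each injection site as λ = −m = ln(2)/half-life, with m the slope from the model refitted in the revised population. Equivalently, write CB_t = C_0·exp(−ln(2)·t/half-life). State that t is the actual number of days since the baseline sample, in the same unit as the half-life. This is one line of wording, with no new data, no change to the design and no cost.
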